6.0 DOSING DELAYS/DOSE MODIFICATIONS

6.1 Dose Modifications/Delays for Toxicities Encountered During Therapy.

Table 6. Dose Modifications and Delays for Entospletinib and Obinutuzumab

Description		Grade	Dose modification
Non-hematologic	Initial or first recurrence	3-4 and clinically significant*	Hold treatment with both drugs and evaluate at least weekly as clinically indicated. Delay dose until toxicity resolves to Grade ≤ 2 , then complete current cycle or start next cycle with reduction in entospletinib by one dose level (Table 5)
	Second recurrence		Discontinue
Description		Grade	Dose modification
Hematologic	Initial or first recurrence	As defined in DLTs: Grade 4 neutropenia lasting > 7 days. Grade 4 thrombocytopenia/ anemia or grade 3 thrombocytopenia with bleeding or any requirement for platelet transfusion, unexplained by underlying disease Febrile neutropenia	Hold treatment with both drugs. Initiate at least weekly CBC checks, growth factor (G-CSF allowed at Investigator's discretion) and transfusion support as clinically indicated until resolved to Grade 1 or $> 75\%$ baseline. May continue this cycle or start next cycle with reduction in entospletinib by one dose level (Table 5).
	Second recurrence		Discontinue

*Not clinically significant includes: Grade 3 nausea or vomiting occurring without optimal treatment; asymptomatic Grade 3 laboratory abnormalities that are not life-threatening and respond to treatment; grade 3 obinutuzumab infusion reactions; grade 4 infusion reaction, which will be an investigator dependent decision

Note: Grading of non-hematologic toxicities will be according to NCI CTCAE v.4.03. Grading of hematologic toxicity will be according to the 1996 modified NCI-WG criteria for CLL/SLL, updated in 2008.

Table 7. Restarting Doses of Entospletinib after Treatment Interruption for Drug-Related Toxicity

Entospletinib dose at the time of first toxicity	1 st reduction	2 nd reduction
200 mg daily	Discontinue	-
200 mg BID	200 mg daily	Discontinue
400 mg BID	200 mg BID	200 mg daily

There are NO dose reductions for obinutuzumab.

In cases where toxicities led to dose reduction, dose re-escalation of entospletinib may be considered in subsequent cycles at the discretion of the treating physician after at least two cycles of study therapy are well tolerated without any recurrent toxicities at the reduced dose.

Treatment delays due to hematologic, non-hematologic and renal toxicities are permitted for up to 28 days from the end of a previous 28-day cycle. For longer delays, the study treatment will end (Section 5.5). In case of a treatment delay subsequent study assessment days will be adjusted accordingly. If a treatment delay occurs, both drugs (entospletinib and obinutuzumab) will be delayed.

For less severe toxicities not described above, holding one or both drugs and dose reductions are discouraged, but remain at the discretion of the treating physician.

Treatment with entospletinib and obinutuzumab will be discontinued if one of the following occurs despite dose modifications:

1. Second recurrence of grade 3-4 non-hematologic toxicities.
2. Second recurrence of grade 3-4 hematologic toxicities.
3. Treatment delay of >28 days from the end of a previous 28-day cycle.

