5.2 Definition of Dose-Limiting Toxicities (DLT)

Dose escalation will stop for DLT defined as any of the following occurring with cycle 1 (including run-in) in the dose escalation phase, deemed related (possibly, probably or definitely) to the study drug:

1. Non-hematologic toxicity: all \geq Grade 3 toxicities *except*
 - a. Grade 3 nausea, vomiting or diarrhea reversible within 72 h with supportive care
 - b. Grade 3 infusion-related toxicity
 - c. Asymptomatic Grade 3-4 laboratory abnormalities that are reversible to \leq Grade 2 within 72 hours (for example, Grade 3-4 elevation of uric acid, AST, ALT, changes in phosphorus and magnesium levels, changes in glucose levels)
 - d. Grade 3 only: tumor lysis syndrome (TLS) or hyponatremia (equals Na 120-130 mEq/L)
2. Hematologic toxicity:
 - a. Grade 4 neutropenia lasting more than 7 days in a subject with ANC $> 1500 \mu\text{L}$ before beginning therapy
 - b. Febrile neutropenia of any duration (ANC $< 500/\mu\text{L}$, fever $> 38.5^\circ\text{C}$)
 - c. Grade 4 thrombocytopenia/anemia or grade 3 thrombocytopenia with bleeding or any requirement for platelet transfusion, unexplained by underlying disease

Grading of toxicities will be according to NCI CTCAE v.4.03. Grading of hematologic toxicity in patients with CLL/SLL will be conducted according to the 1996 modified NCI-WG criteria for CLL/small lymphocytic lymphoma (SLL), updated in 2008 [41]. A toxicity deemed to be unrelated to therapy (such as hip fracture due to a traumatic fall), will NOT be considered as a DLT.

Patients who completed 1 cycle of study treatment will be evaluable for dose escalation decision purpose. Patients who receive $< 50\%$ of doses of entospletinib or < 2 doses of obinutuzumab during cycle 1 and who do not experience DLT, will NOT be evaluable for dose escalation decision purpose and will be replaced. Intra-patient dose escalation will be allowed to the level of MTD, once MTD has been determined.

Management and dose modifications associated with the above adverse events are outlined in Section 6.

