Institutional guidelines may be used for obinutuzumab administration. We suggest this general approach: vital signs should be taken every 15 minutes for the first hour of infusion until stable, then every 30 minutes until the completion of infusion. Pulse oximetry on room air should be performed at baseline and as needed if dyspnea occurs. Epinephrine 1 mg/ml, diphenhydramine 50 mg IV and hydrocortisone 100 mg IV should be readily available during obinutuzumab infusion. For first infusion (C1D1), obinutuzumab is administered at a rate of 25 mg/hour for four hours. On C1D2 obinutuzumab is started at 25 mg/hr (50 mg/hr if no IRR occurred on C1D1) and rate escalated by 50 mg/hour every 30 minutes until a maximum rate of 400 mg/hour provided no infusion reaction occurs. For subsequent infusions, infusion may be started at 50 mg/hour (100 mg/hour if no reactions with previous infusion) and increased by 100 mg/hour increments every 30 minutes until a maximum rate of 400 mg/hour.

If a patient experiences an infusion reaction of any grade during infusion, adjust the infusion as follows:

Grade 4 (life threatening): Stop infusion immediately and permanently discontinue obinutuzumab therapy.

Grade 3 (severe): Interrupt infusion and manage symptoms. Upon resolution of symptoms, consider restarting obinutuzumab infusion at no more than half the previous rate (the rate being used at the time that the infusion reaction occurred) and, if patient does not experience any further infusion reaction symptoms, infusion rate escalation may resume at the increments and intervals as appropriate for the treatment cycle dose. Permanently discontinue obinutuzumab treatment if patients experience a Grade 3 infusion-related symptom at re-challenge.

For CLL patients only, the Day 1 infusion rate may be increased back up to 25 mg/hr after 1 hour but not increased further.

Grade 1 – 2 (mild to moderate): Reduce infusion rate or interrupt infusion and treat symptoms. Upon resolution of symptoms, continue or resume infusion and, if patient does not experience any further infusion reaction symptoms, infusion rate escalation may resume at the increments and intervals as appropriate for the treatment cycle dose.

For CLL patients only, the Day 1 infusion rate may be increased back up to 25 mg/hr after 1 hour but not increased further.

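### Section 5.3.2.3 and the Table 6 footnote give unreconciled instructions on obinutuzumab after a Grade 4 infusion reaction

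*Combined protocol and SAP*

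**What the plan says.** Section 5.3.2.3 (Infusion-Related Reactions) introduces its advice with "Institutional guidelines may be used for obinutuzumab administration. We suggest this general approach". It then turns to reactions during the infusion with the instruction "If a patient experiences an infusion reaction of any grade during infusion, adjust the infusion as follows". The line for the highest grade reads "Grade 4 (life threatening): Stop infusion immediately and permanently discontinue obinutuzumab therapy".

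Table 6 in section 6.1 is titled for both entospletinib and obinutuzumab. Its non-hematologic row applies to toxicities that are "3-4 and clinically significant", with an asterisk leading to a footnote. The footnote opens "Not clinically significant includes: Grade 3 nausea or vomiting occurring without optimal treatment", goes on to Grade 3 obinutuzumab infusion reactions, and ends with "grade 4 infusion reaction, which will be an investigator dependent decision".

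Section 5.2 takes "Grade 3 infusion-related toxicity" out of the dose-limiting toxicities. It makes no such exception for Grade 4.

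**The concern.** The two places deal with the same event and do not mention each other. One tells the site to end obinutuzumab. The other places the event in a list headed as not clinically significant and leaves it to the investigator.

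The footnote is not a remote piece of text. Section 5.1 sends readers to Section 6 for dose modifications of both drugs, and section 5.2 closes by sending them there for management. A site that follows those pointers reaches the footnote without passing through 5.3.2.3.

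What is at stake is consistent handling of a reaction that the protocol itself labels life threatening. Differences in handling would also carry into the obinutuzumab exposure and treatment-discontinuation data.

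**Working it through.** No sample size, power or error rate is involved, so the check is a comparison of the texts.

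1. **Section 5.3.2.3 on its own.** The opening sentence is permissive, but the Grade 4 line is an instruction with no stated discretion. The Grade 3 text in the same place is softer: it asks the site to consider restarting once symptoms resolve. The Grade 4 outcome for obinutuzumab is permanent discontinuation.

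2. **Table 6, if the investigator judges the reaction not clinically significant.** The non-hematologic row is not triggered. Table 6 then requires no hold, and it says nothing about ending obinutuzumab.

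3. **Table 6, if the investigator judges the reaction clinically significant.** At an initial event or first recurrence, the row holds both drugs until the toxicity falls to Grade 2 or lower. The cycle is then completed or the next one started, with entospletinib lowered by one dose level. Discontinuation appears only at the second recurrence, and the list after Table 7 repeats this for non-hematologic toxicities.

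4. **Comparison.** Neither branch of Table 6 leads to permanent discontinuation of obinutuzumab at first occurrence. The branch in step 2 is silent on it. The branch in step 3 contains text under which treatment resumes. Only a site that also consults 5.3.2.3, and treats it as overriding, arrives at that section's outcome.

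5. **Scope of the footnote.** It does not say that it concerns only the hold and the entospletinib reduction. The table title names both drugs and the row holds both.

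6. **Cross-check with 5.2.** A related Grade 4 infusion reaction during the run-in or cycle 1 of dose escalation meets the definition of dose-limiting toxicity, because only Grade 3 is exempt. That agrees with 5.3.2.3 in treating Grade 4 as more serious than Grade 3. Section 5.2 classifies events for escalation decisions, whereas the footnote defines a trigger for dose modification, so the two do not contradict each other.

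**The case against.** The best defence is that the texts divide the work. On this view 5.3.2.3 governs the infusion and obinutuzumab, while the footnote only decides which events start the Table 6 hold and entospletinib reduction. Two details support it. Section 6.1 states that obinutuzumab has no dose reductions. The footnote also lists Grade 3 infusion reactions, for which 5.3.2.3 has its own rules, including permanent discontinuation if a Grade 3 symptom returns at re-challenge. The footnote may therefore be removing infusion reactions from Table 6 because they are handled elsewhere. This reading is possible, but nothing in the text states it, and the resume-after-hold wording remains if the row is triggered. The defence shows how the wording could be repaired; it does not show that the wording is already clear.

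Three further points stand in part.

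- A reader might infer that the protocol declares Grade 4 reactions insignificant. It does not go that far. The qualifier attached to Grade 4 most naturally means that the investigator judges significance.
- A reader might call 5.3.2.3 a mandatory rule that the footnote breaks. The section's permissive opening weakens that claim, and it means that some variation between sites is tolerated by 5.3.2.3 itself. Correcting the footnote alone would therefore not be enough.
- Section 5.6 requires immediate notice to the lead investigator of life-threatening complications. This gives central visibility of the event but sets no rule for what happens next.

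**Conclusion.** The inconsistency is real and should be corrected. Section 5.3.2.3 ends obinutuzumab after a Grade 4 infusion reaction. Table 6 and its footnote leave the event to the investigator and, in one branch, permit treatment to resume. No sentence says which text prevails.

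Its size is qualitative. The documents give no Grade 4 infusion-reaction rate: they report Grade 3-4 reactions combined (21% with chlorambucil in previously untreated patients) and a single Grade 4 withdrawal among five CLL patients in a Phase I study. A reader might assume a rate and compute the chance of at least one such event in this trial. That would show only that an event may occur, not that it would be mishandled, so no probability is offered.

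A reader might also infer that 5.2 is a third conflicting rule, or that dose-escalation counts are compromised. The documents do not support either. The footnote does not purport to change the definition of dose-limiting toxicity, and no effect on the maximum tolerated dose, the complete-response test or its error rate has been shown.

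The conclusion rests on reading the footnote as written, without an unstated limit to entospletinib.

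**What to change.** Reconcile section 5.3.2.3 and the Table 6 footnote so that one rule governs obinutuzumab after a Grade 4 infusion reaction. The clinical team decides which rule that is. In the same revision:

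- state whether the footnote concerns only the Table 6 trigger for holding treatment and reducing entospletinib;
- state whether the permissive opening of 5.3.2.3 extends to the Grade 4 line;
- add a cross-reference in each section to the other;
- add a sentence to the footnote that it does not alter classification of dose-limiting toxicity under 5.2, whose definition can stay as it is.

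The cost is a wording amendment with the usual committee and IRB approval. Design, sample size and analysis are unchanged.

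### Section 6.1 defines the toxicities that end treatment in two different ways, and Tables 6 and 7 part company where no lower entospletinib dose exists

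*Combined protocol and SAP*

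**What the plan says.** Three parts of section 6.1 bear on when treatment stops.

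**Table 6.** The hematologic row covers events "As defined in DLTs: Grade 4 neutropenia lasting > 7 days", together with Grade 4 thrombocytopenia or anemia, Grade 3 thrombocytopenia with bleeding or a platelet transfusion requirement, and febrile neutropenia. The non-hematologic row covers events that are "3-4 and clinically significant". Its footnote lists exclusions, beginning "Not clinically significant includes: Grade 3 nausea or vomiting occurring without optimal treatment" and including asymptomatic Grade 3 laboratory abnormalities that are not life-threatening and respond to treatment. At the initial event and the first recurrence, both drugs are held and entospletinib is reduced by one dose level; the reader is sent to Table 5 for the levels. At the second recurrence the entry is to discontinue, with no drug named.

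**Table 7**, titled "Restarting Doses of Entospletinib after Treatment Interruption for Drug-Related Toxicity", concerns entospletinib only. From 200 mg daily the first step is to discontinue. From 200 mg BID the steps are 200 mg daily, then discontinue. From 400 mg BID they are 200 mg BID, then 200 mg daily.

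**The closing text.** For events outside Table 6 it says: "For less severe toxicities not described above, holding one or both drugs and dose reductions are discouraged", leaving them to the treating physician. The numbered list follows: "Treatment with entospletinib and obinutuzumab will be discontinued if one of the following occurs despite dose modifications". Its first two items are "Second recurrence of grade 3-4 non-hematologic toxicities" and "Second recurrence of grade 3-4 hematologic toxicities".

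**The concern.** The list uses Table 6's vocabulary of recurrences but drops its restrictions. Neither the DLT-type limit on hematologic events nor the clinical-significance limit on non-hematologic events appears. A treating physician who works from the list, and another who works from Table 6, can therefore reach opposite decisions on permanent withdrawal of both drugs for the same patient. The paragraph just before the list makes this harder to reconcile: for the lesser events it discourages even a temporary hold.

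A second, narrower problem is the join between Tables 6 and 7. Table 6 calls for a one-level reduction at occurrences where Table 7 has no lower level to offer.

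Treatment is planned for at least 12 cycles, and CR is the primary endpoint of Phase II. What is at stake is exposure, the count of discontinuations for toxicity, and consistent handling across physicians and sites.

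**Working it through.** The plan gives no figure to reproduce here, so the check sets the three rules side by side. I count the initial event as occurrence 1, the first recurrence as 2 and the second recurrence as 3, and treat the episodes as the same toxicity.

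| Case | Table 6 | Table 7 (entospletinib only) | Numbered list, read literally | Consistent? |
|---|---|---|---|---|
| Three uncomplicated Grade 3 neutropenia episodes, or Grade 4 lasting 7 days or less without fever | Not triggered | Not reached unless the physician chooses to interrupt | Both drugs stop at occurrence 3 | No |
| Three asymptomatic, treatable, non-life-threatening Grade 3 laboratory abnormalities | Excluded by footnote | As above | Both drugs stop at occurrence 3 | No |
| Table 6 event, first toxicity at 200 mg daily, occurrence 1 | Reduce one level | Discontinue | No action yet | No |
| First toxicity at 200 mg BID, occurrence 1 | Reduce one level | 200 mg daily | No action yet | Yes |
| First toxicity at 200 mg BID, occurrence 2 | Reduce one level | Discontinue | No action yet | No |
| First toxicity at 400 mg BID, occurrences 1 and 2 | Reduce one level each time | 200 mg BID, then 200 mg daily | No action yet | Yes |
| First toxicity at 400 mg BID, occurrence 3 | Discontinue, no drug named | No entry | Both drugs stop | Yes, apart from the unnamed drug |

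Two separate findings follow.

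1. **Event definition.** The list is wider than Table 6 for both toxicity classes (first two rows).
2. **Dose steps.** Table 7 departs from Table 6 in 2 of its 3 dose rows. From 200 mg daily it stops entospletinib at occurrence 1 rather than 3, which is 3 - 1 = 2 occurrences before the list acts. From 200 mg BID it stops at occurrence 2, which is 3 - 2 = 1 before. In both rows this is exactly where no lower planned level exists (section 5.1.1, Table 2). Nothing states what then happens to obinutuzumab.

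**Cross-references.** Both rows of Table 6 cite Table 5 for the dose levels. Table 5 (section 5.3.2.3) is the obinutuzumab premedication schedule; the reductions are in Table 7.

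**How many patients.** The first conflict needs three episodes, all outside Table 6. The protocol reports no such count. The nearest figure is in section 2.3.2.2, Study BO20999 Phase I, relapsed/refractory CLL on obinutuzumab alone: 9 of 13 patients had Grade 3-4 neutropenia, 7 with one event and 2 with more than one.

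- Share with more than one event: 2/13 = 15.4%.
- Scaled to the 17 Phase II patients in the sample-size calculation: 17 x 2/13 = 2.6 with at least one recurrence.
- Those with three or more episodes are not reported; in that study they could number at most 2 of 13.

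This is a rough guide only: 13 patients, several dose levels, no entospletinib, and neutropenia alone.

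**The case against.** The best defence is that the list only restates the last row of Table 6 and makes explicit that both drugs stop. It stands in the same section, reuses the term second recurrence, and is introduced by a clause about dose modifications. On that reading only toxicities already handled under Table 6 count. The reading is natural, but the text does not state it.

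A reader might infer the opposite extreme: that the list clearly captures every Grade 3-4 event. The documents do not support that either. The list contains no such word, and its opening clause permits a narrower sense.

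A reader might also infer that the clause is empty for lesser events because they never lead to a modification. That is wrong. Section 6.1 leaves holds and reductions for them to the physician, section 5.3.2.6 allows delays to be considered for Grade 3 or 4 neutropenia, and the Day 1 neutrophil criterion in section 10.2.2 can itself delay a cycle. These provisions do not resolve the ambiguity. They add a third reading, in which a discretionary hold or delay brings a lesser event within the list.

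On Table 7, the defence is largely right. It supplies the levels that Table 6 calls for, and its discontinue entries fall only where a reduction cannot be carried out. A reader might infer that Table 7 is a general rule for stopping both drugs earlier; it is not. It covers entospletinib only, and its 400 mg BID row agrees with Table 6 and the list. What remains is that Table 6 does not acknowledge the exception and that obinutuzumab is left unaddressed.

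**Conclusion.** The contradiction is real as written. Table 6 and the list define the events that end treatment differently, and the qualifying clause permits a reconciliation without stating one. Tables 6 and 7 disagree for a first toxicity at 200 mg daily or 200 mg BID. For Phase II patients starting at the RP2D, that second conflict arises only if the RP2D is one of those two doses. It already applies to Phase I patients at those levels.

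The number of patients affected cannot be derived from the documents and is probably small. Section 2.3.2.2 gives Grade 3-4 neutropenia of 27.5% with obinutuzumab 1000 mg alone and 34% with chlorambucil, and a reader might infer that 17 x 0.275 = 4.7 to 17 x 0.34 = 5.8 patients fall under the conflict. Those figures come from previously untreated patients and count anyone with at least one event, whereas the conflict requires three.

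A reader might also infer damage to the primary test. No power, alpha or endpoint definition changes. An effect on CR through altered exposure is possible but cannot be estimated from the documents.

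This is a consistency defect in a rule for permanent withdrawal. It deserves correction, but it does not undermine the design. The conclusion rests on a literal reading of the list and on counting recurrences of the same toxicity.

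**What to change.** Reconcile Table 6, Table 7 and the numbered list in section 6.1:

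- Use one event definition, with the same grades and the same exclusions, in all three places.
- State for each entospletinib dose which drug stops at which occurrence, and name the drug in Table 6's second-recurrence entries.
- State what applies to entospletinib and to obinutuzumab when no lower entospletinib level exists.
- Correct the two references to Table 5 so that they point to Table 7.

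The sponsor decides which rule is intended; this review takes no position on that. The cost is amendment wording in section 6.1, with no added patients, visits or tests.
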